7.1.1 Pre-Imaging Period

7.1.1.1 Screening Assessments (Day -60 to Day 1)

The Screening assessments must be completed within 60 days of the Day 1 Visit. Patients will not be required to have undergone US or sestamibi imaging prior to FCH PET.

- Written informed consent will be obtained prior to performing any study related activities.
- Inclusion/exclusion criteria will be checked.

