4. False negative: No evidence of parathyroid adenoma on FCH PET independent of findings at time of surgery.

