9.2.2 Sestamibi evaluation

In patients who had a sestamibi study performed prior to the fluorocholine imaging study, we will use the original dictated report from the sestamibi. This will be done as there may be significant bias in the interpretation of the sestamibi studies if re-interpreted. Identical to the PET data, the study reports, will be used to characterize location (left/right, location with respect to the thyroid, or description of location if atypical). All suspected lesions as well as the single most suspicious lesion will be recorded. The sensitivity from this analysis will be used as our comparator for the FCH PET. For each reader, lesions will be characterized as follows:

1. True positive: Location of the suspected adenoma on sestamibi correlates with location of an abnormal parathyroid at time of surgery. For a patient with multiple hyperplastic glands, only one gland needs to correlate for the patient to count as a true positive.
 - a. For analysis, adenomas described as arising in the mid thyroid bed will be considered correct if located in either the inferior or superior bed.
2. False positive: Location of the suspected adenoma on sestamibi does not agree with location of an abnormal parathyroid at time of surgery.
3. True negative: There are no true negatives as patients with primary hyperparathyroidism have near 100% incidence of hyperplastic adenomas.
4. False negative: No evidence of parathyroid adenoma on sestamibi independent of findings at time of surgery.

The performance of the imaging modalities will be quantified by sensitivity, specificity, positive predictive value and negative predictive value.

Performance will be assessed using surgery as the gold standard with postoperative normalization of calcium as the study endpoint as described above. For this study to have a positive outcome, two of the three FCH PET readers have to have a sensitivity that is 10% greater than that of sestamibi imaging. For statistical analysis we will use the McNemars's test with a p-value of 0.05 for significance. We will also compare the sensitivity of 18F-fluorocholine to the predetermined detection sensitivity of 70%. Again, two of the three FCH PET readers have to have a sensitivity that is 10% greater than 70% (ie 80%). We will also report an interreader variability for the FCH PET reads using a Fleiss's Kappa. The baseline characteristics will be reported as follows: continuous parametric data will be reported as mean

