+- standard deviation, continuous non-parametric data as medians with interquartile range. Dichotomous data will be reported as proportions. Patients with missing imaging results or missing data on the primary endpoint will be excluded from the study.

In patients who do not subsequently undergo parathyroidectomy, we will use the dictated reports to determine the detection sensitive for parathyroid adenomas.

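### Operated patients whose FCH scan gave no usable result may leave the sensitivity denominator, because the plan does not say how failed or uninterpretable scans are scored

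*Combined protocol and SAP*

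**What the plan says.** The missing-data rule for efficacy is one sentence at the end of Section 9.2.2: "Patients with missing imaging results or missing data on the primary endpoint will be excluded from the study". It names no modality and no cause, and it does not define a missing result. No analysis that counts the excluded patients as failures goes with it.

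Section 9.2.1 sorts each blinded reader's FCH result into true positive, false positive, true negative (which the plan says cannot occur) or false negative. The last class reads: "False negative: No evidence of parathyroid adenoma on FCH PET independent of findings at time of surgery". An incomplete or uninterpretable scan is not mentioned, nor is the case where one reader cannot interpret a scan that the other two can. Sections 4.4 and 6.1 provide for one imaging session and one injection, and no repeat scan is described.

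For the comparator, "we will use the original dictated report from the sestamibi". The same four classes apply, including "False negative: No evidence of parathyroid adenoma on sestamibi independent of findings at time of surgery". Sestamibi is optional: "Patients will not be required to have undergone US or sestamibi imaging prior to FCH PET".

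For primary endpoint 1, "two of the three FCH PET readers have to have a sensitivity that is 10% greater than that of sestamibi imaging", with McNemar's test at 0.05. For primary endpoint 2, two of three readers must reach 80%, which the plan derives as 10 points above a fixed 70%.

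**The concern.** For a surgical patient who has been injected, a scan that fails or cannot be read means no localisation. A sensitivity computed only among usable scans answers a narrower question than how often FCH correctly localises disease in an operated patient who received it. Sections 8.1 and 9.3 keep every injected patient in the safety analysis, but the efficacy rule can remove some of them.

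The direction is fixed: dropping a patient whom FCH did not localise can only raise observed FCH sensitivity relative to counting a miss. Endpoint 2 is decided on an observed percentage alone. Endpoint 1 needs an observed margin as well as a test. Near either boundary, one or two patients can decide the outcome. Because a missing result is undefined, the classification could also be settled after the surgical findings are known.

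**Working it through.** **Inputs.** From Section 9.1: sestamibi 70%, FCH 85%, dropout 10%, 65 patients in the initial cohort, 140 in total. From Section 9.2.2: the 80% mark and the 10% margin, read as percentage points because the plan turns 70% into 80%. Not in the documents: f, the share of operated patients whose FCH scan is failed or uninterpretable. I assume 1% to 10%. The 10% dropout is not split by cause, so it does not supply f.

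**The plan's own figure.** A one-sample normal approximation, one-sided 0.05, 87% power, 70% against 85%:

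n = [(1.645 × √(0.70 × 0.30) + 1.126 × √(0.85 × 0.15)) / 0.15]² ≈ 59.4, so 60.

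With dropout this gives 67 (60/0.9) or 66 (60 × 1.1), close to the stated 65. I therefore use 85% and 70% as the planning rates below.

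**Endpoint 2, fixed 80% mark.** Take sensitivity as correctly localised patients over operated patients analysed. Then

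sensitivity with failures counted = sensitivity among readable scans × (1 − f).

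| f | 85% among readable becomes | 80% among readable becomes |
|---|---|---|
| 1% | 84.2% | 79.2% |
| 2% | 83.3% | 78.4% |
| 5% | 80.8% | 76.0% |
| 10% | 76.5% | 72.0% |

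The planned 85% falls to 80% at f = 1 − 0.80/0.85 = 5.9%.

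In whole patients, taking 90% of 140 (126) and of 65 (58.5, so 58) and assuming all of them are operated:
- 126 patients, 2 failures: 100/124 = 80.6% passes; 100/126 = 79.4% does not.
- 58 patients, 1 failure: 46/57 = 80.7% passes; 46/58 = 79.3% does not.

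These cases were chosen at the boundary to show how few patients matter there.

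**Endpoint 1, against sestamibi.** Exclusion removes the patient's sestamibi result too, so the effect depends on m, the sestamibi sensitivity in patients whose FCH scan failed. With 85% and 70% among the remaining pairs:

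difference with failures counted = 0.15 × (1 − f) − f × m.

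| f | failures excluded | m = 0.70 | m = 0 |
|---|---|---|---|
| 1% | 15.0 points | 14.2 | 14.9 |
| 2% | 15.0 | 13.3 | 14.7 |
| 5% | 15.0 | 10.8 | 14.3 |
| 10% | 15.0 | 6.5 | 13.5 |

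At m = 0.70 the difference reaches 10 points at f = 0.05/0.85 = 5.9%. At m = 0 the effect is small.

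**McNemar's test.** A patient who is sestamibi-positive with a failed FCH scan is a discordant pair against FCH, and exclusion deletes that pair. As an illustration, discordant counts of 14 and 4 give an exact two-sided p of 0.031. Restoring one such patient gives 14 and 5, with p = 0.064. The uncorrected chi-square for 14 and 5 is 9²/19 = 4.26, still below 0.05, so the version of the test matters, and the plan does not state it.

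**The case against.** The plan never says that an unreadable FCH scan is a missing result. If images exist, three readers interpret them, and a reader who can localise nothing could fairly be scored under the FCH false-negative rule. On that reading only scans that yielded no images are excluded, and f may be very small. At f = 1% the effect is under one point. Under the planning rates f must reach about 5.9% before a verdict changes, and the one-patient examples sit at the boundary. Sensitivity among completed scans is also a legitimate quantity if it is labelled as such.

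All of this stands. It makes the inflation conditional but does not supply the missing definition, and the conditional effect runs in one direction only.

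A reader might go further and infer that the plan treats the two tests unequally: a failed FCH scan is dropped, while a non-diagnostic sestamibi study, which has a dictated report, is scored as a miss. If equal shares of both tests failed, that would widen the planned 15-point gap to 0.85 − 0.70 × 0.98 = 16.4 points at 2% and 0.85 − 0.70 × 0.95 = 18.5 points at 5%. The documents do not support it. The exclusion sentence names no modality, the two false-negative rules differ only in the name of the test, and Section 9.2.2 says the sestamibi reports are to be characterised in the same way as the PET data. Non-diagnostic studies are not mentioned for either test.

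**Conclusion.** The plan has a complete-case rule and no stated scoring for failed, incomplete or uninterpretable scans. To the extent that such FCH scans are treated as missing, FCH sensitivity is overstated by f × 85% relative to counting misses: 0.85 points at 1%, 1.7 at 2%, 4.25 at 5% and 8.5 at 10%. Against sestamibi the overstatement has the same size if sestamibi localises 70% of the patients whose FCH scan failed, and is much smaller if it localises none of them.

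This rests on three assumptions: that failures occur at a rate the documents do not give, that they fall under the exclusion sentence, and that the planning rates hold. Unequal treatment of the two modalities is a possible reading but not a stated rule, and the conclusion about the 80% mark does not need it. The point is worth settling before analysis. On the documents alone it does not show that either primary result would be wrong.

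**What to change.** Replace the exclusion sentence, for the primary endpoints, with rules to this effect:

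- **Endpoint 2.** Every injected patient with a surgical reference is in the denominator. An FCH scan that was not completed, or that a reader cannot interpret, counts as not localised for that reader.
- **Endpoint 1.** The analysis set is injected, operated patients who had a sestamibi study. A failed or non-diagnostic FCH read and a non-diagnostic sestamibi report both count as not localised. Patients with no sestamibi study are outside this paired comparison. The restriction is needed because sestamibi is optional and McNemar's test requires both results.
- **Reporting.** Tabulate failed and non-diagnostic examinations by modality and, for FCH, by reader. Present the analysis that excludes them as a sensitivity analysis.

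Fix the classification before reads are matched to surgical findings. The cost is a few lines of SAP text and one table, with no change to study procedures. The downside is that FCH sensitivity may come out slightly less favourable.

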3.3 Secondary endpoint

Detection rate of 18F-fluorocholine PET in patients who have not undergone surgical resection.

4 Study Design

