7.1.2 Imaging Period

7.1.2.1 Study Procedures (Day 1)

- Administration of 18F-fluorocholine
 - The one-time nominal injected dose will be 4 to 7 mCi containing FCH. Patient shall begin imaging between 20 and 60 minutes after the injection of the radiopharmaceutical.
- Imaging using either PET/CT or PET/MRI
 - Coverage for the scan will extend from the base of the skull to the pulmonary artery. PET acquisition will be for a minimum of 10 minutes per bed position.
 - A dictated report will be made of the imaging findings and be provided to the endocrine surgeons. FCH PET imaging results will be used in conjunction with other imaging modalities, including available ultrasound and sestamibi studies, to direct surgical intervention.

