9.2 Analyses Plans

At the time of the imaging study, each scan will be interpreted by a nuclear medicine physician, who will be fully cognizant of the clinical, imaging and laboratory data. Focal uptake on choline PET will be reported by location (left/right, location with respect to the thyroid, or description of location if atypical), along with measured SUVmax. These reads will not be used for evaluation of the primary endpoint.

9.2.1 18F-fluorocholine blinded reads

All 18F-fluorocholine imaging data will be anonymized and collected. PET data will be interpreted by three different board certified nuclear medicine readers in a random order at separate reading sessions. Prior to interpretation a training data set using choline PET studies not included in the study will be used to train the readers. Clinical information will not be available to the readers at time of interpretation. Cross sectional imaging from the PET will be available for anatomic correlate, but no other imaging study will be available. Each study will be characterized by location (left/right, location with respect to the thyroid, or description of location if atypical). "Atypical" refers to adenomas that are not in the thyroid bed and would include the mediastinum. All suspected lesions as well as the single most suspicious lesion will be recorded. For example, in the setting of multiple parathyroid adenomas, one lesion will be reported by the readers as most suspicious.

The location of each adenoma that is surgically confirmed will be marked in the identical fashion (left/right, location with respect to the thyroid [ie inferior or superior], or description of location if atypical). For each reader, lesions will be characterized as follows:

1. True positive: Location of the suspected adenoma on FCH PET correlates with location of an abnormal parathyroid at time of surgery. For a patient with multiple hyperplastic glands, only one gland needs to correlate for the patient to count as a true positive.
 - a. For analysis, adenomas described as arising in the mid thyroid bed will be considered correct if located in either the inferior or superior bed.
2. False positive: Location of the suspected adenoma on FCH PET does not agree with location of an abnormal parathyroid at time of surgery.
3. True negative: There are no true negatives as patients with primary hyperparathyroidism have near 100% incidence of hyperplastic adenomas.

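### The detection rate in unoperated patients is taken from one fully informed clinical report, although three blinded reads of the FCH scans are planned and not limited to operated patients

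*Combined protocol and SAP*

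**What the plan says.** - Section 3.3 defines the secondary endpoint: "Detection rate of 18F-fluorocholine PET in patients who have not undergone surgical resection".
- The end of section 9.2.2 names the data source: "In patients who do not subsequently undergo parathyroidectomy, we will use the dictated reports to determine the detection sensitive for parathyroid adenomas". It does not name the modality of these reports, and it stands in the sestamibi section.
- Section 7.1.2.1 describes the FCH report: "A dictated report will be made of the imaging findings and be provided to the endocrine surgeons". The findings are then used with other available imaging to direct surgery.
- Section 9.2 says that each scan is interpreted at the time of imaging by a physician "who will be fully cognizant of the clinical, imaging and laboratory data". It adds: "These reads will not be used for evaluation of the primary endpoint". No reason is given.
- Section 9.2.1 describes a second set of reads: "All 18F-fluorocholine imaging data will be anonymized and collected. PET data will be interpreted by three different board certified nuclear medicine readers". These readers see no clinical information and no imaging other than the cross-sectional images acquired with the PET.
- Section 9.2.2 bases the success rule on the three FCH PET readers, with surgery as the gold standard. Just before the sentence on unoperated patients, it excludes from the study any patient with missing imaging results or missing primary-endpoint data.

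**The concern.** The two patient groups are measured under different reading conditions. The operated group is judged by three readers without clinical data. The unoperated group is judged by one reader who has everything, including any ultrasound or sestamibi result. Such a reader can call equivocal uptake positive because another test points to the same place, so the rate may partly reflect other tests.

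The primary sensitivity exists only in operated patients. The secondary endpoint is the plan's only result in the remaining patients. Anyone who sets the two side by side would be comparing reading conditions as well as patients.

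The sentence in 9.2.2 also words the measure as a sensitivity, while 3.3 calls it a detection rate. Without surgery there is nothing to show whether a positive call is in the right place.

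**Working it through.** The plan states no expected rate, sample size or test for this endpoint, so there is no figure to reproduce. The check sets the sections side by side and then uses two illustrations with assumed inputs.

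**1. Which reports are meant?** Section 3.3 concerns FCH PET, and 7.1.2.1 describes a dictated FCH report. The FCH clinical report is therefore the natural reading of 9.2.2, although the text should say so. The one reason the plan gives for relying on dictated reports, bias on re-interpretation, is given for sestamibi. No reason is given for using them for FCH, where separate blinded reading is the primary method.

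**2. Do blinded reads exist for these patients?** Section 9.2.1 speaks of all FCH imaging data, and the Abstract (Efficacy Assessments) says that the FCH studies are read by three blinded readers. Neither limits this to operated patients, but neither says outright that unoperated patients' scans are read. This is a reasonable inference, not a stated fact.

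**3. Is a positive-scan rate a sensitivity?** Assume that 85% of patients have a positive call in the right place, and let the share with a wrong-place call be 0%, 5% or 10%. The positive-scan rate is 85 + 0 = 85%, 85 + 5 = 90% or 85 + 10 = 95%, while the correctly located share stays at 85%. Without surgery only the first quantity can be seen. This is true of blinded reads as well.

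**4. What does selection for surgery do?** The report goes to the surgeons, so it may influence who is operated on. Assume that 85% of dictated reports are positive. Let s1 and s0 be the surgery rates after a positive and a negative report:

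unoperated positivity = 0.85(1 − s1) / [0.85(1 − s1) + 0.15(1 − s0)]

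- s1 = 0.90, s0 = 0.60: 0.085 / (0.085 + 0.060) = 0.085 / 0.145 = 59%.
- s1 = 0.90, s0 = 0.75: 0.085 / (0.085 + 0.0375) = 0.085 / 0.1225 = 69%.
- s1 = s0: 85%.

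Now assume that a blinded reader is positive in 95% of report-positive and 15% of report-negative scans:

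- First case: (0.085 × 0.95 + 0.060 × 0.15) / 0.145 = 0.08975 / 0.145 = 62%.
- Second case: (0.085 × 0.95 + 0.0375 × 0.15) / 0.1225 = 0.086375 / 0.1225 = 71%.
- Third case: 0.85 × 0.95 + 0.15 × 0.15 = 83%.

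| Surgery rate after positive / negative report | Dictated rate, unoperated | Blinded rate, unoperated |
|---|---|---|
| 90% / 60% | 59% | 62% |
| 90% / 75% | 69% | 71% |
| equal | 85% | 83% |

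The spread down each column is selection for surgery, and changing the reader leaves most of it. The last row also gives the rates in all imaged patients, which selection does not affect. There the informed rate is the higher one under these assumptions. In the two selected groups it is the lower one. The direction of the net difference in unoperated patients therefore cannot be predicted from the documents.

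**5. Does the endpoint have a population?** Unoperated patients have no surgical reference and hence no primary-endpoint result. Taken literally, the exclusion sentence in 9.2.2 removes exactly the patients that 3.3 needs.

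**The case against.** The strongest reply is that 3.3 is a stand-alone descriptive rate. The plan compares it with nothing and does not use it to extend the operated-only sensitivity to other patients. The FCH result is used in practice together with other imaging, so a rate from the informed report describes the scan as used. This stands as a reason to keep the dictated-report rate. It is not a reason to omit the blinded rate if those reads are available.

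A second reply is that blinded reads of unoperated patients' scans are not guaranteed. The Abstract ties those reads to pathology, and 9.2.1 defines true and false positives by surgical location. This also stands: coverage of every scan is inferred and should be stated.

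Three stronger readings are tempting, and the documents do not support them:

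- A reader might infer that the plan itself rejects the clinical reads as biased. Section 9.2 bars them from the primary endpoint but gives no motive.
- A reader might take the 59% to 85% range as the size of the informed-reading effect. It shows selection for surgery under assumed rates.
- A reader might infer that blinded reads would make the unoperated and operated groups comparable. They align the reading conditions only. Selection and the missing surgical reference remain.

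**Conclusion.** The point holds as a cheap improvement to a descriptive secondary endpoint. The endpoint rests on one informed reader and the primary result on three blinded readers. The plan gives no reason for the difference, and the blinded data should already exist. The rate can be raised by knowledge of other findings, and it is not like-for-like with the operated group.

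The size of the reading effect cannot be derived from the documents, because they give no agreement between informed and blinded reads and no surgery rates. The conclusion rests on two readings of the text: that the dictated reports in 9.2.2 are the FCH reports, and that the blinded reads in 9.2.1 cover all imaged patients. A reader might go further and infer that the trial's main conclusion is affected. It is not, because the primary analysis and success rule do not use these reports.

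**What to change.** 1. In 3.3 and 9.2.2, compute the positive-scan (detection) rate for each blinded reader in unoperated, operated and all imaged patients, and show the three side by side. The table does not remove selection for surgery. It makes it visible, and the all-imaged rate does not depend on who was operated on.
2. Keep the dictated-report rate as a descriptive supplement, and state that it comes from the FCH report.
3. Use the term detection rate throughout, not sensitivity, for patients without a surgical reference.
4. State in 9.2.1 that unoperated patients' scans are included in the blinded reads.
5. Reconcile the exclusion sentence in 9.2.2 with 3.3, for example by limiting it to the primary analysis set.

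The cost is SAP wording and one table. No new reads are needed if 9.2.1 covers every scan. If it was meant for operated patients only, the cost is up to three extra reads per unoperated patient.
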